### 6.5.3 Intake of prohibited concomitant medication having impact on efficacy

Drug groupings, individual drugs and manual review will be used to identify prohibited concomitant medications that were defined in the protocol to influence efficacy. All here listed drug groupings/names were reported in OASIS 1-3 studies, although other medications may also be prohibited per the protocol.

In terms of the efficacy endpoints related to the change from baseline in HF frequency

1. Any intake of prohibited medication during Week 1 that has an effect on HF will be considered an intercurrent event.
2. For weeks 4, 8, and 12, not only intake in the respective week but also, intake that occurred prior to Week 4, 8, and 12 should be considered as an intercurrent event if within the washout period of the prohibited drug.

The list of prohibited concomitant medication with the pre-defined washout period for their effect will be reviewed during blind review of the data and finalized prior to unblinding.

**Table 6–5: Preliminary list of prohibited concomitant medication by drug grouping (can be updated during blind review meeting)**

DGCODEL0	DGNAME0	DGCODEL1	DGNAME1	DGCODEL2	DGNAME2	Duration of impact with respect to efficacy* (considered up to 12 weeks**)
		108	Drugs acting on gonadotropin-releasing hormone (GnRH) receptors	109	GnRH agonists	From 1st dose to 12 weeks after the last dose
		108	Drugs acting on gonadotropin-releasing hormone (GnRH) receptors	110	GnRH antagonists	From 1st dose to 12 weeks after the last dose
		5	Hormone replacement therapy	2	Oestrogens	1, From 1st dose to 4 weeks after the last dose if the route is vaginal, intravaginal,

						cutaneous, nasal or transdermal 2, From 1st dose to 8 weeks after the last dose if the route is oral, sublingual or intrauterine 3, From 1st dose to 12 weeks or longer, if the route is subcutaneous or intradermal.
		5	Hormone replacement therapy	3	Progestogens	1, From 1st dose to 4 weeks after the last dose if the route is vaginal, intravaginal, cutaneous, nasal or transdermal 2, From 1 st dose to 8 weeks after the last dose if the route is oral, sublingual or intrauterine 3, From 1st dose to 12 weeks or longer, if the route is subcutaneous or intradermal.
		772	Cancer therapies	738	Endocrine antineoplastic therapy	From 1st dose to 12 weeks after the last dose
1633	Drugs for psychiatric disorders	111	Antidepressants	114	Monoamine oxidase (MAO) inhibitors, non-selective	From 1st dose to 4 weeks after the last dose
1633	Drugs for psychiatric disorders	111	Antidepressants	115	Monoamine oxidase A (MAO-A) inhibitors	From 1st dose to 4 weeks after the last dose
1633	Drugs for psychiatric disorders	111	Antidepressants	112	Non-selective monoamine reuptake inhibitors	From 1st dose to 4 weeks after the last dose
1633	Drugs for psychiatric disorders	111	Antidepressants	113	Selective serotonin reuptake inhibitors (SSRI)	From 1st dose to 4 weeks after the last dose
45	Drugs interacting with CYP3A	240	CYP3A inducers	225	Moderate CYP3A inducers	From 1st dose to 4 weeks after the last dose. Considered not to have an influence on efficacy, if route is auricular(otic) or ophthalmic.
45	Drugs interacting with CYP3A	240	CYP3A inducers	265	Strong CYP3A inducers	From 1st dose to 4 weeks after the last dose
1633	Drugs for psychiatric disorders	111	Antidepressants	1830	Antidepressant Serotonin Norepinephrine Reuptake Inhibitors (SNRI)	From 1st dose to 4 weeks after the last dose

\*In this column, the terms "1st dose" and "last dose" both refer to the start date and stop date of certain doses of concomitant medication. If the dose was changed, a new start date and/or stop date were reported.

\*\* No further differentiation if duration of impact is longer than 12 weeks since ICEs are considered in the analysis only for the first 12 weeks of the study.

In addition the following concomitant medications are considered prohibited.

**Table 6–6: Preliminary list of prohibited concomitant medication by drug names (can be updated during the blind review meeting)**

Any additional condition, so that considered as prohibited and considered as intercurrent event	WHO Drug Name	WHO Drug Record Number	WHO Drug Sequence Number 1	WHO Drug Sequence Number 2	Duration of impact with respect to efficacy* (considered up to 12 weeks**)
If newly started or dose modified during the first 12 weeks of study period	ARMOUR THYROID	000537	01	011	From 1st dose to 12 weeks after the last dose
If newly started or dose modified during the first 12 weeks of study period	NATURE THROID	000537	01	027	From 1st dose to 12 weeks after the last dose
If newly started or dose modified during the first 12 weeks of study period	LEVOTHYROXINE	000680	01	001	From 1st dose to 12 weeks after the last dose
If newly started or dose modified during the first 12 weeks of study period	L-THYROXINE	000680	01	006	From 1st dose to 12 weeks after the last dose
If newly started or dose modified during the first 12 weeks of study period	L-THYROXIN	000680	01	014	From 1st dose to 12 weeks after the last dose
If newly started or dose modified during the first 12 weeks of study period	LEVAXIN	000680	02	002	From 1st dose to 12 weeks after the last dose
If newly started or dose modified during the first 12 weeks of study period	SYNTHROID	000680	02	005	From 1st dose to 12 weeks after the last dose
If newly started or dose modified during the first 12 weeks of study period	EUTHYROX	000680	02	007	From 1st dose to 12 weeks after the last dose
If newly started or dose modified during the first 12 weeks of study period	THYROXIN	000680	02	014	From 1st dose to 12 weeks after the last dose
If newly started or dose modified during the first 12 weeks of study period	LEVOTHYROXINE [LEVOTHYROXINE SODIUM]	000680	02	020	From 1st dose to 12 weeks after the last dose
If newly started or dose modified during the first 12 weeks of study period	THYREX	000680	02	028	From 1st dose to 12 weeks after the last dose
If newly started or dose modified during the first 12 weeks of study period	THYROHORMONE	000680	02	029	From 1st dose to 12 weeks after the last dose
If newly started or dose modified during the first 12 weeks of study period	T4	000680	02	031	From 1st dose to 12 weeks after the last dose
If newly started or dose modified during the first 12 weeks of study period	LETROX	000680	02	046	From 1st dose to 12 weeks after the last dose
If newly started or dose modified during the first 12 weeks of study period	UNITHROID	000680	02	052	From 1st dose to 12 weeks after the last dose

12 weeks of study period					
If newly started or dose modified during the first 12 weeks of study period	LEVOTIROXINA [LEVOTHYROXINE SODIUM]	000680	02	054	From 1st dose to 12 weeks after the last dose
If newly started or dose modified during the first 12 weeks of study period	L-THYROXIN HENNING	000680	02	058	From 1st dose to 12 weeks after the last dose
If newly started or dose modified during the first 12 weeks of study period	TIROXIN [LEVOTHYROXINE SODIUM]	000680	02	062	From 1st dose to 12 weeks after the last dose
If newly started or dose modified during the first 12 weeks of study period	L THYROXIN	000680	02	070	From 1st dose to 12 weeks after the last dose
If newly started or dose modified during the first 12 weeks of study period	EUTIROX	000680	02	074	From 1st dose to 12 weeks after the last dose
If newly started or dose modified during the first 12 weeks of study period	LEVOTHYROXIN	000680	02	081	From 1st dose to 12 weeks after the last dose
If newly started or dose modified during the first 12 weeks of study period	TIROSINT	000680	02	087	From 1st dose to 12 weeks after the last dose
If newly started or dose modified during the first 12 weeks of study period	EUTHYROX N	000680	02	138	From 1st dose to 12 weeks after the last dose
If newly started or dose modified during the first 12 weeks of study period	LEVOTIROXIN	000680	02	145	From 1st dose to 12 weeks after the last dose
If newly started or dose modified during the first 12 weeks of study period	L THYROX	000680	02	163	From 1st dose to 12 weeks after the last dose
If newly started or dose modified during the first 12 weeks of study period	TIROSINT SOL	000680	02	219	From 1st dose to 12 weeks after the last dose
If newly started or dose modified during the first 12 weeks of study period	LIOTHYRONINE	001433	01	001	From 1st dose to 12 weeks after the last dose
If newly started or dose modified during the first 12 weeks of study period	LIOTHYRONIN	001433	02	020	From 1st dose to 12 weeks after the last dose
	CLONIDINE	001711	01	001	From 1st dose to 4 weeks after the last dose
	CLONIDINE HYDROCHLORIDE	001711	02	001	From 1st dose to 4 weeks after the last dose
	DIXARIT	001711	02	002	From 1st dose to 4 weeks after the last dose
	CLONIDINE HCL	001711	02	048	From 1st dose to 4 weeks after the last dose
	CANNABIS SATIVA	002377	01	001	From 1st dose to 4 weeks after the last dose
	CANNABIS SATIVA	002377	01	002	From 1st dose to 4 weeks after the last dose

	MARIJUANA	002377	01	002	From 1st dose to 4 weeks after the last dose
	CBD OEL	002377	08	003	From 1st dose to 4 weeks after the last dose
	OXYBUTIN	005389	02	057	From 1st dose to 4 weeks after the last dose
	DRIPTAN	005389	02	126	From 1st dose to 4 weeks after the last dose
	GABAPENTIN	010030	01	001	From 1st dose to 4 weeks after the last dose
	NEURONTIN [GABAPENTIN]	010030	01	002	From 1st dose to 4 weeks after the last dose
	GABRION	010030	01	024	From 1st dose to 4 weeks after the last dose
	GABAPENTINE	010030	01	045	From 1st dose to 4 weeks after the last dose
	GABA [GABAPENTIN]	010030	01	226	From 1st dose to 4 weeks after the last dose
	PREGABALIN	016141	01	001	From 1st dose to 4 weeks after the last dose
	LYRICA	016141	01	002	From 1st dose to 4 weeks after the last dose
	PRAGIOLA	016141	01	249	From 1st dose to 4 weeks after the last dose
	EGZYSTA	016141	01	314	From 1st dose to 4 weeks after the last dose
	PREATO	016141	01	722	From 1st dose to 4 weeks after the last dose
	CANNABIDIOL	079492	01	001	From 1st dose to 4 weeks after the last dose
If newly started or dose modified during the first 12 weeks of study period	THYRONAJOD	109689	02	006	From 1st dose to 12 weeks after the last dose
If newly started or dose modified during the first 12 weeks of study period	LEVOTHYROXINE;POTASSIUM IODIDE	109689	03	001	From 1st dose to 12 weeks after the last dose
If newly started or dose modified during the first 12 weeks of study period	LEVOTHYROXINE AND LIOTHYRONINE [LEVOTHYROXINE;LIOTHYRONINE]	131345	01	008	From 1st dose to 12 weeks after the last dose
If newly started or dose modified during the first 12 weeks of study period	NOVOTHYRAL	131345	03	007	From 1st dose to 12 weeks after the last dose

\*In this column, the terms "1st dose" and "last dose" both refer to the start date and stop date of certain doses of concomitant medication. If the dose was changed, a new start date and/or stop date were reported.

\*\* No further differentiation if duration of impact is longer than 12 weeks since ICEs are considered in the analysis only for the first 12 weeks of the study.

## 6.6 Appendix 6: Population characteristics

In general, descriptive statistics will be presented for variables defined in this section. For continuous variables, number of observations, mean, standard deviation, minimum, median, and maximum will be presented. For categorical variables, number and percentage of participants will be presented. Listings will be provided as appropriate.

### 6.6.1 Demographics and baseline characteristics

All demographic and baseline characteristics will be summarized by treatment group and overall. The descriptive statistics will be presented for the SAF, FAS and BAS.

Demographic and baseline assessments to be summarized will include:

- Age (at inclusion), region/country, race, ethnicity
- Categorized age
  - <40 years, 40-49 years, 50-59 years, 60-65 years, >65 years
- Weight (kg), height (cm), body mass index (BMI; kg/m^2)
- Categorized BMI (< 18.5, 18.5 to < 25, 25 to < 30, ≥ 30 kg/m^2)
- Smoking history (Never, Former, Current)
- Level of education

Demographic and baseline characteristics will be summarized also for the following subgroups (only for FAS):

- Region (North America, rest of the world)
- Race
- Ethnicity
- Smoking history (Never, Former, Current)
- BMI (< 18.5, 18.5 to < 25, 25 to < 30, ≥ 30 kg/m^2)
- Moderate to severe HFs at baseline (< 35, ≥ 35)

### 6.6.2 Reproductive and Menstrual History and History of menopause hormone therapy

*Reproductive and menstrual history* will include information on number of pregnancies, number of births, years being amenorrheic and number of participants with hysterectomy or oophorectomy. Hysterectomy or oophorectomy are based on Medical History. (For hysterectomy the PTs Hysterectomy, Hysterosalpingectomy, Hysterosalpingo-oophorectomy and Radical hysterectomy are considered. For oophorectomy the PTs Hysterosalpingo-oophorectomy, Oophorectomy, Oophorectomy bilateral, Salpingo-oophorectomy, Salpingo-oophorectomy bilateral, Salpingo-oophorectomy unilateral are considered.) These variables will be analyzed descriptively, separately for each treatment group and overall based on the SAF, FAS and BAS.

*History of menopause hormone therapy* will include information on history of menopause hormone therapy, contra-indications for hormonal treatment, personal risk factors for hormonal treatment and benefit risk assessment. This data will be shown in the listing only.

### 6.6.3 Protocol deviations

Important deviations from the protocol and validity findings and the resulting assignment of participants to the analysis sets (see Section 4) are agreed upon in the blind review meeting (BRM). The documentation of important deviations, validity findings and the assignment of participant data to analysis sets will be performed according to the sponsor's applicable Standard Operating Procedures and/or Instruction Manuals. The definition for important deviations and validity findings will be provided in the 'Specification of assessment criteria and identification requirements' before unblinding the data.

Identification of important deviations and validity findings will be done periodically while the study is running, concluding with the completion of the final list during the BRM. Any changes to the statistical analysis prompted by the results of BRM will be documented in an amendment and, if applicable, in a supplement to this SAP.

The list of important deviations and validity findings will only be final after assessment of conditional findings, which are validity findings that can only be identified after unblinding of study treatment.

### 6.6.4 Medical history

For medical history MedDRA (current version at the time of analysis) will be used. Medical history findings (i.e., previous diagnoses, diseases or surgeries) not pertaining to the study indication, starting before start of treatment and considered relevant to the study will be tabulated by primary SOC and PT by treatment group and overall. Medical history will be presented for SAF.

[figure not shown]
All new or worsened findings after start of study treatment should be documented on the AE eCRF page.

### 6.6.5 Prior, concomitant and post-treatment medication

For prior/concomitant/post-treatment medications, the following definitions in accordance with the Global Standards Catalogue (v4.0 or later) will be used in the analysis (see [Figure 6–1](#)):

- Prior medication: Medication taken before start of the study drug intake, (regardless of when it ended).
- Concomitant medication: Medication taken during treatment phase, i.e. between first and last study drug intake (regardless of when it started or ended).
- Post-treatment medication: Start of medication is after last study drug intake.

Missing dates will be imputed as described in Section [5.1.1](#).

**Figure 6–1: Categories of concomitant medication (example).**

Categories are prior medication (A, B, C), concomitant medication (B, C, D, E) and post-treatment medication (F). Source: Global Standards Catalogue V4.0

Medication, recorded as prior, concomitant or post-treatment medication in the eCRF, will be coded according to the World Health Organization Drug Dictionary WHODRUG Global (current version at the time of analysis)), to the respective Drug Codes with their corresponding Anatomical Therapeutic Chemical (ATC) classification.

The number of participants taking prior, concomitant or post-treatment medication will be analyzed using frequency tables and shown by treatment group and overall. Analysis of prior, concomitant and post-treatment medication will be done on the SAF.

### 6.6.6 Insomnia Severity Index (ISI)

The ISI is a seven-item instrument that quantifies the participant perception of insomnia severity, along with the impact of insomnia on daytime functioning in adults in the last two weeks (Bastien et al. 2001). The seven questions are with respect to:

1. difficulty falling asleep
2. difficulty staying asleep
3. problems waking up too early
4. satisfaction/dissatisfaction with current sleep pattern
5. noticeability of sleep problems by others
6. worries/distress caused by the sleep difficulties
7. extent of interference of sleep difficulties with daily functioning.

It is scored on a five-point Likert scale from 0 to 4 depending on the item:

- Items 1-3: 0='none' to 4='very severe'
- Item 4: 0='very satisfied' to 4='very dissatisfied'
- Item 5: 0='not at all noticeable' to 4='very much noticeable'
- Item 6: 0='not at all worried' to 4='very much worried'
- Item 7: 0='not at all interfering' to 4='very much interfering' (Item 7)

The scores for each item are summed to produce the total score (maximum 28) which allow categorization of severity of insomnia.

Total score categories:

0–7 = No clinically significant insomnia

8–14 = Subthreshold insomnia

15–21 = Clinical insomnia (moderate severity)

22–28 = Clinical insomnia (severe)

The absolute values for Total score will be analyzed at baseline by descriptive statistical methods as described in section [5.1](#) by treatment group and overall. Summary statistics of Total score across the different severity categories by treatment group will be provided with frequency tables as well. In addition, Severity of insomnia presented in categories above will be summarized with frequency tables by treatment group and overall.

## 6.7 Appendix 7: Coding conditions applicable for AESI

AESI	Search
Potential AESI – Liver event  “Any condition triggering close liver observation” according to protocol Section 10.5 results in true AESIs of liver events. The search specified here is beyond the protocol definition of the AESI and will be considered together with the assessment by the Liver Safety Monitoring Board to determine a true AESI.	SMQ Cholestasis and jaundice of hepatic organ SMQ Drug related hepatic disorders – severe events only SMQ Liver related investigations, signs and symptoms SMQ Liver-related coagulation and bleeding disturbances  In addition, include AESIs ticked at AE-CRF.
Somnolence or fatigue	a) Somnolence MLG: PT Somnolence PT Hypersomnia b) Fatigue (MGL Decreased general strength and energy) PT Asthenia PT Decreased activity PT Fatigue PT Fatigue management PT Mental fatigue PT Physical deconditioning PT Sluggishness  In addition to MLGs above, include, PT Sleep disorder due to general medical condition, hypersomnia type
Phototoxicity	BMQ Photosensitivity reactions
Post-menopausal uterine bleeding	MLG Female genital tract bleeding PT Abnormal uterine bleeding PT Abnormal withdrawal bleeding PT Cervix haematoma uterine PT Cervix haemorrhage uterine PT Coital bleeding PT Haematocoele female PT Haematosalpinx PT Haemorrhagic ovarian cyst PT Ovarian haematoma PT Ovarian haemorrhage PT Postmenopausal haemorrhage PT Unexpected vaginal bleeding on hormonal IUD PT Uterine haematoma PT Uterine haemorrhage PT Vaginal haematoma PT Vaginal haemorrhage PT Vulval haematoma PT Vulval haematoma evacuation PT Vaginal haemorrhage PT Withdrawal bleed

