### **8.2.7 Transvaginal ultrasound (TVU)**

- Ultrasound examination should be performed by a physician/examiner well experienced in gynecology or with corresponding qualification based on local clinical practice. TVU is not required in participants who had both a total hysterectomy and a bilateral salpingo-oophorectomy.
- The following safety parameters will be measured and recorded:
  - Endometrial thickness (measured in the medio-sagittal section as double-layer in millimeters)
  - Overall safety assessment of the pelvic organs, especially for evaluation of the uterus, ovaries (including diameters as well as details of cyst like structures, if applicable) and fallopian tubes (abnormalities to be reported as AE/SAE)
- In case of any suspicious finding, further diagnostic investigations should be performed at the discretion of the investigator.
- The minimum documentation will include printouts and/or electronic format with images from the ultrasound machine showing the endometrium in sagittal section and both ovaries. The images have to be labeled unambiguously, containing at least the study number, participant number, time point, endometrial thickness, and laterality

(left/right) for ovaries. If the printouts are on thermo-sensitive paper, they need to be copied as they will fade over time.

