### 8.3.6 Adverse Events of Special Interest

The following are defined as AESI in this study, if the event takes place after the first intake of study intervention:

- Any condition triggering close liver observation according to Section 10.5.

Any increase in liver enzymes meeting the following criteria needs to be reported as an adverse event to the sponsor within 24 hours of the investigator's awareness for expedited reporting to the health authorities:

- ALT and/or AST  $>8x$  ULN OR
- ALT and/or AST  $>3x$  ULN with total bilirubin  $>2x$  ULN

The investigator may consider whether the observed increase in liver values would qualify as SAE.

- Somnolence or fatigue: Mild somnolence has been identified as a possible adverse reaction to elinzanetant. Participants will be instructed neither to drive nor operate machinery if they experience somnolence or fatigue. As a precautionary measure, participants are dosed in the evening before going to bed.
- Phototoxicity: A signal with respect to potential phototoxicity warrants monitoring of participants for skin reactions to sunlight. In case such a reaction occurs, exposure to strong sunlight should be avoided.
- Post-menopausal uterine bleeding: Any participants experiencing post-menopausal bleeding after randomization should undergo a transvaginal ultrasound with subsequent investigation and management (including endometrial biopsy, if indicated) according to the investigator's clinical judgement and usual practice (unexplained

post-menopausal bleeding prior to randomization will exclude the participant from the study).

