### 5.6.2 Adverse Events

Adverse events (AEs) will be collected from the start of study intervention until the last follow-up. (Serious) Adverse events ((S)AEs) which are related to protocol required study procedures (e.g., (S)AE related to invasive study procedures) will be recorded as (S)AEs from the signing of the ICF (pre-treatment (S)AEs). Any medical occurrences/conditions that begin

in the period between signing Informed consent form (ICF) and the start of study intervention, and which are not related to a protocol-required study procedure, will be recorded on the Medical History/Current Medical Conditions, not as AEs.

All AEs will be summarized by treatment group using the Medical Dictionary for Regulatory Activities (MedDRA) preferred terms (PT) grouped by system organ class (SOC) (the current version at the time of analysis) and classified into pre-treatment, treatment-emergent (TEAE) and post-treatment AEs. Incidences of TEAEs and TESAEs per 100 person-years will be summarized by treatment group. The rate per 100 person-years is calculated as

Rate per 100 person-years = number of subjects / (total drug exposure in years / 100),  
where 365.25 days are taken as one year.

A TEAE is defined as any adverse event occurring or worsening on or after the date of the first dose of study drug up to 14 days after the date of the last dose of study drug. AEs will be flagged as TEAE except for AEs for which there is clear evidence that the AE starts before date of first study drug intake (pre-treatment AEs) or after the date of last study drug intake + 14 days (post-treatment AEs).

If the severity of a previously reported event worsens or if the relationship to study intervention/protocol required procedures changes, two separate events should be reported.

Worsening of an AE is defined as follows:

- AE intensity is worsened (e.g., moderate to severe)
- AE changed to a serious event
- AE ends with death

In case an AE starts before the date of last study drug intake + 14 days and worsens after last study drug intake + 14 days will be considered as two AEs, a TEAE and a post-treatment AE.

Partially missing onset AE date will be imputed following a worst-case approach as described in section [5.1.1](#).

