In case of events with different intensity within a participant, the maximum reported intensity will be used. If the same event is considered as both unrelated and related to the study drug within a participant, the event will be reported as related to study drug. If the drug relationship is missing, the event will be considered as being related to the study drug.

The tabulation will follow in principle the Bayer Global Standard Tables catalogue (v4.0 or later). SAEs and Adverse events of special interest (AESI) will be summarized in the same way as described for TEAEs. A separate table summarizing TEAEs that occurred in more than 5% of the participants will be provided.

In addition, participants with a COVID-19 as an adverse event will be listed.

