### **Adverse events of special interest (AESI)**

AESIs will be identified by Standardized MedDRA Query (SMQ) searches, PTs and also via eCRF as further detailed in Section [6.7](#). The following AEs are considered:

1. Any condition triggering close liver observation (as listed in Protocol section 10.5)

2. Somnolence or fatigue
3. Phototoxicity
4. Post-menopausal uterine bleeding (women without hysterectomy are considered)

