#### **5.6.3.7 Transvaginal ultrasound**

Number and percentage of participants with ultrasound performed and result of overall assessment at each visit (baseline, Week 52 and EoT) will be presented by treatment group.

Endometrial thickness will be summarized by treatment group for each visit, including change from baseline where appropriate, using descriptive statistics for women without hysterectomy.

Number and percentage of participants that developed ovarian cyst during the study will be presented by treatment group.

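### The search for the AESI post-menopausal uterine bleeding covers the whole female genital tract, so the count under that label could exceed the number of women with the protocol AESI (minor)

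*SAP*

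**What the plan says.** Protocol 8.3.6 makes post-menopausal uterine bleeding an AESI. Its working text is somewhat wider than its title: "Any participants experiencing post-menopausal bleeding after randomization should undergo a transvaginal ultrasound with subsequent investigation and management".

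SAP 5.6.2 keeps the name and restricts the population: "Post-menopausal uterine bleeding (women without hysterectomy are considered". It identifies AESIs by dictionary searches set out in SAP 6.7 and also through the eCRF.

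The bleeding row of SAP 6.7 is headed with a grouping for bleeding of the female genital tract and lists preferred terms (PTs). One stretch reads "PT Haematocoele female PT Haematosalpinx PT Haemorrhagic ovarian cyst PT Ovarian haematoma PT Ovarian haemorrhage". Another reads "PT Vaginal haemorrhage PT Vulval haematoma PT Vulval haematoma evacuation PT Vaginal haemorrhage PT Withdrawal bleed".

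Tabulation follows the general adverse event rules of SAP 5.6.2: "SAEs and Adverse events of special interest (AESI) will be summarized in the same way as described for TEAEs". For TEAEs that means PTs within system organ class and exposure-adjusted rates: "Incidences of TEAEs and TESAEs per 100 person-years will be summarized by treatment group".

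The liver row of SAP 6.7 is handled differently. It is titled as a potential AESI, states that its search goes beyond the protocol definition, and brings in the Liver Safety Monitoring Board's assessment to decide which cases are true AESIs. The SAP version history also records an added frequency table for actual close liver observations, because the AESI table held potential cases only.

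**The concern.** A label that names one event sits on a search that captures others. An ovarian haematoma or a haematosalpinx is not uterine bleeding, and it is not post-menopausal bleeding in the sense of Protocol 8.3.6, where the woman bleeds and is then investigated. Limiting the AESI to women without hysterectomy does not remove the mismatch, because a woman with a uterus can still have an ovarian, tubal or vulval event.

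The documents also show how such a term could arise in a woman who never bled. Protocol 8.2.7 has the ultrasound examiner assess "ovaries (including diameters as well as details of cyst like structures, if applicable) and fallopian tubes (abnormalities to be reported as AE/SAE". Ultrasound is scheduled at Week 52 or end of treatment. An incidental haemorrhagic cyst seen there, if coded to its listed term within the treatment-emergent window, would count as post-menopausal uterine bleeding.

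At stake is the figure most likely to be quoted for this AESI: the number of women per arm and the rate per 100 person-years. The PT rows would show the non-uterine terms. They cannot be summed to give the number of women with any matching term, because one woman can have several PTs.

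**Working it through.** **Step 1: count the terms.** The bleeding row of SAP 6.7 has 20 PT entries. Vaginal haemorrhage appears twice, so 19 are distinct. The SAP states no term count to reproduce.

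**Step 2: classify the 19 against Protocol 8.3.6** (any post-menopausal bleeding, under a uterine title).

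| Group | Terms | Number |
|---|---|---|
| Clearly not the AESI | haematocoele female, haematosalpinx, haemorrhagic ovarian cyst, ovarian haematoma, ovarian haemorrhage | 5 |
| Lower-tract haematoma, need not be the AESI | vulval haematoma, vulval haematoma evacuation, vaginal haematoma | 3 |
| Fits the protocol text | abnormal uterine bleeding, abnormal withdrawal bleeding, cervix haematoma uterine, cervix haemorrhage uterine, coital bleeding, postmenopausal haemorrhage, unexpected vaginal bleeding on hormonal IUD, uterine haematoma, uterine haemorrhage, vaginal haemorrhage, withdrawal bleed | 11 |

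5 + 3 + 11 = 19.

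**Step 3: check the ultrasound route against the time window.** SAP 5.6.2 counts events up to 14 days after the last dose as treatment-emergent. Footnote a of Protocol Table 1–2 places the end-of-treatment visit within 14 days of stopping drug for early discontinuers. A finding at that visit can therefore fall inside the window.

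**Step 4: effect of one affected woman.** An affected woman is one whose only listed terms come from the eight. The percentage effect is 100 / N, where N is the number of women without hysterectomy in her arm. The documents plan 300 per arm but do not give the hysterectomy share, so 10 to 30% is assumed; 0% is the limiting case.

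For the rate, SAP 5.6.2 divides the number of women by total drug exposure in years / 100. Exposure is approximated from SAP 3 for the elinzanetant arm: 300 at start, 270 at month 3, 240 at month 6 and 210 at month 12. Loss is assumed linear between these points:

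(285 × 0.25) + (255 × 0.25) + (225 × 0.5) = 71.25 + 63.75 + 112.5 = 247.5 person-years.

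Exposure is scaled to women without hysterectomy, assuming that the denominator follows the restriction.

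| Hysterectomy share (assumed) | N | Person-years | One woman adds, percentage points | One woman adds, per 100 person-years |
|---|---|---|---|---|
| 0% | 300 | 247.5 | 0.33 | 0.40 |
| 10% | 270 | 222.75 | 0.37 | 0.45 |
| 20% | 240 | 198.0 | 0.42 | 0.51 |
| 30% | 210 | 173.25 | 0.48 | 0.58 |

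These figures show the size of one miscount. They do not estimate how many will occur.

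**The case against.** The strongest reply is that the breadth is open and cautious. The row shows the name of the wider grouping and lists every PT. The search is prespecified and the same in both arms, and over-inclusion is the safer direction for a descriptive safety search. This stands, and it is why the broad search should be kept.

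A second reply is that the narrower figure can be recovered. Any non-uterine PT would be visible in the tables, and SAP 5.1 provides subject data listings from which someone could count the women. Table specifications are in a separate document and might contain a narrower row. This stands in part: the SAP itself specifies no narrower total. Identification through the eCRF is a further source but removes none of the listed PTs, and how it works for bleeding is not spelled out.

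Third, the ultrasound route is conditional. It needs a new finding, reported as an adverse event, coded to a listed term, inside the window, in a woman with a uterus and no bleeding term. Women with cysts needing work-up to rule out malignancy were excluded at screening (Protocol 5.1, inclusion criterion 5, footnote). New cysts also have their own table in SAP 5.6.3.7: "Number and percentage of participants that developed ovarian cyst during the study will be presented by treatment group". All of this stands, and it limits the likely size.

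Fourth, the boundary involves judgement. Only the five ovarian, tubal and haematocoele terms are clear-cut. Whether a term requires a uterus cannot be the test, since vaginal haemorrhage and coital bleeding do not require one and are kept. The test used here is the protocol's working text, and vulval and vaginal haematomas are treated alike.

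**Conclusion.** The search is wider than the AESI it is named for, and neither a caveat nor a narrower count corrects this. The participant total and the rate under the label could exceed the number of women with the protocol AESI. The excess is unknown and may be zero. Each affected woman adds 0.33 to 0.48 percentage points and 0.40 to 0.58 per 100 person-years. This assumes a hysterectomy share of 0 to 30%, linear loss between the planned exposure points, and a denominator limited to women without hysterectomy.

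A reader might infer three stronger things, none of which the documents support.

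- **That the total is wrong as it stands.** It is unaffected unless some woman has only terms from the eight, and no incidence is given.
- **That the share of terms measures the error.** 5 of 19 (26%) or 8 of 19 (42%) is a share of dictionary entries, not of women or events.
- **That a treatment comparison or the endometrial safety conclusion is at risk.** The search is the same in both arms, safety is descriptive (Protocol 9.4.5), no decision rule uses this AESI, and the endometrium is assessed directly by biopsy and ultrasound.

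Severity is minor.

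**What to change.** Before unblinding:

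1. In SAP 6.7, keep the full list and label the bleeding row as a broad search wider than the protocol definition, as the liver row already is.
2. Add one participant-level count by arm, in women without hysterectomy, of women with any uterine, cervical, vaginal, coital, postmenopausal or withdrawal bleeding term. Leave out the ovarian, tubal and haematocoele terms and the vulval and vaginal haematoma terms. These are the 11 terms in the last row of the classification table. The three haematoma terms are a judgement, so that choice should be fixed in writing at the same time.
3. Delete the second vaginal haemorrhage entry. This is editorial and changes no count.

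The cost is one label and one table row, with no new data. Sensitivity is kept because the broad search stays beside the narrow one, and ovarian cysts keep their own table. The downside is a second number for the same AESI, which needs a footnote saying how the two differ.
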